15.0 Drug Information

The literature reports no deleterious effect was revealed in toxicity testing of ^{18}F -DOPA-PET, and concludes the toxicological safety of the product is guaranteed given the toxicity data of the various potential impurities [72]. ^{18}F -DOPA-PET is currently in production at this institution, and is used to image Parkinson's patients to study the ^{18}F -DOPA uptake in the caudate nucleus and putamen.

16.0 Statistical Considerations and Methodology

16.1 Study Overview:

This is a one-stage Simon's Optimal Phase-II study [73] with an interim analysis that will compare confirmed-progression free survival at 6 months (CPFS6) for Grade IV MGMT un-methylated glioma patients after radiation therapy targeting volumes designed with both ^{18}F -DOPA PET and conventional MR image information with historical controls from Mayo Clinic Rochester patients treated on NCCTG clinical trials. To determine if the integration of ^{18}F -DOPA imaging into a dose escalation strategy for RT/TMZ therapy significantly improves tumor control, we will analyze confirmed-progression free survival for patients treated with PET-guided dose escalation and will compare against historical controls for Grade IV MGMT un-methylated patients treated at Mayo Clinic either with standard of care RT+TMZ then TMZ-alone or on the NCCTG clinical trials N057K or N0874. These trials have completed accrual. These trials all use identical MRI-based definitions of $\text{GTV}_{1\text{MR}}$ and $\text{GTV}_{2\text{MR}}$, and the same CTV and PTV expansions as the proposed study (Section 7.0, [Table 1](#)). On all trials, PTV1 and PTV2 were treated to 50 Gy and 60 Gy respectively, and radiation was delivered with concomitant TMZ (75 $\text{mg}/\text{m}^2/\text{day}$ x 6 weeks) and subsequently adjuvant TMZ (150-200 mg/m^2 days 1-5 x 6 cycles). Progression-free survival was a secondary endpoint in all these trials, and each specified the same MR imaging follow-up regimen as the proposed study. Moreover, all patients had both acute and late toxicities recorded at each of their pre-defined follow-up and treatment visits. All of the treatment dosimetry and MR imaging is archived within the Mayo Clinic electronic medical record, which will facilitate greatly our planned analysis of patterns of failure.

16.11 The primary endpoint of this trial is the proportion of Grade IV MGMT un-methylated patients that experience confirmed-progression-free survival at 6 months (CPFS6) based on our hypothesis that the combination of more accurate delineation of high density tumor by ^{18}F -DOPA PET combined with dose escalation will improve overall tumor control. One of our neuro-radiologists, [REDACTED] or [REDACTED], will review all cases to define the date of radiographic progression, with analysis of historical controls falling under IRB #12-004263. With the close imaging follow-up mandated on all these clinical trials, we will be able to robustly evaluate progression. Both Grade III and IV glioma patients will be enrolled on this clinical trial, however Grade III astrocytomas are relatively rare and not commonly studied in NCCTG or Mayo Clinic trials. At the time of Addendum 8, there exists an Alliance clinical trial lead by a Mayo Clinic Principal Investigator enrolling Grade IV MGMT methylated patients. Enrollment of Grade IV MGMT methylated patients has been reduced compared to the expected rate. Therefore, as of Addendum 8, only the Grade IV MGMT un-methylated patients will be included in the statistical analysis described below. All Grade IV MGMT un-methylated patients meeting eligibility criteria who have signed a consent form and who have begun treatment with ^{18}F -DOPA PET image-guided dose escalation RT will be evaluable for the endpoint.

16.2 Statistical Design

16.21 Decision Rules

An endpoint-evaluable patient is defined to be a patient that is treated with ^{18}F -DOPA PET image-guided dose escalation RT. The primary endpoint is the proportion of grade-IV MGMT un-methylated patients treated with ^{18}F -DOPA PET image-guided dose escalation RT who are alive and do not have confirmed progression within 6 months from the time of craniotomy. A success will be a patient who is alive and does not have confirmed-progression within 6 months from the time of craniotomy. At Mayo Clinic, the 81 Grade IV MGMT un-methylated patients accrued to the two trials listed above, combined with the 14 similar patients not treated on clinical trials had a combined rate of CPFS6 of 59.3%. These patients were newly diagnosed grade-IV MGMT un-methylated patients treated with 3D-conformal or IMRT with TMZ. Therefore the largest success proportion where the proposed treatment regimen would be considered ineffective in this population is 60%, and the smallest success proportion that would warrant subsequent studies with the proposed regimen would be 72.5%. The following Simon's Optimum design requires 45 grade-IV MGMT un-methylated patients to test the null hypothesis that the proportion of successes is at most 60% with an overall significance level (α) of 0.20, and a power of 80% to detect a true success proportion of 72.5%.

16.211 Stage 1: If 15 or fewer successes are observed in the first 25 grade-IV MGMT un-methylated evaluable patients that have been followed for at least 6 months, we will consider this regimen to be ineffective in this patient population. If 16 or more successes are observed in the first 25 evaluable patients we will continue accrual and results will wait until the final analysis.

16.212 Stage 2: After 45 evaluable grade-IV MGMT un-methylated patients are accrued to this study and followed for at least 6 months, if 30 or more successes are observed in the first 45 evaluable patients, we may recommend further testing of this regimen in subsequent studies in this patient population.

16.213 Over Accrual: If more than the target number of Grade-IV MGMT un-methylated patients are accrued, the additional patients will not be used to evaluate the stopping rule or used in any decision making process.

16.214 Note: We will not suspend accrual between stages to allow the first 25 patients to become evaluable, unless undue toxicity is observed.

16.22 Sample Size

The two-stage design to be utilized is fully described in Section 16.21. A minimum of 25 and a maximum of 45 Grade-IV MGMT un-methylated evaluable patients will be accrued to this phase-II study unless undue toxicity is encountered. We anticipate accruing an additional 5 Grade-IV MGMT un-methylated patients to account for ineligibility, cancellation, major treatment violation, or other reasons. We also anticipate accruing a total of 25 Grade-IV MGMT methylated, 12 Grade-IV patients with unknown MGMT status, and 6 grade-III patients. Maximum projected accrual is therefore 87 grade-IV patients and 6 grade-III patients. We anticipate pre-registering 150 patients to register these 93 patients necessary for the study design.

16.23 Accrual Time and Study Duration

Based on institutional experience, we deliver RT on average to 48 Grade IV glioma patients annually, of which about 60% are MGMT un-methylated. Our plan to accrue 14 Grade IV MGMT un-methylated patients per year is based on including about 50% our Grade IV MGMT un-methylated glioma population, which is readily achievable. We plan to accrue patients for Years 1-5.5, leaving the last 6 months of Year 6 for remaining follow-up and analysis. Therefore, the overall study duration is expected to be 72 months.

16.24 Power and Significance Levels

Assuming the number of successes is binomially distributed, the significance level is 0.20 and the probability of declaring that this regimen warrants further studies (i.e. statistical power) under various success proportions and the probability of stopping accrual after the first stage can be tabulated as a function of the true success proportion as shown in the following table.

If the true success proportion is ...	0.55	0.60	0.65	0.70	0.725	0.75
then the probability of declaring that the regimen warrants further studies is ...	0.065	0.195	0.425	0.692	0.804	0.889
and the probability of stopping at stage 1 is ...	0.758	0.575	0.370	0.189	0.122	0.071

16.25 Other Considerations

Adverse events and patterns or failure observed in this study as well as scientific discoveries or changes in standard care will be taken into account in any decision to terminate the study.

16.3 Analysis Plan

The analysis for this trial will commence at the planned timepoints (see 16.2) and at the time the patients have become evaluable for the primary endpoint. Such decision will be made by the Statistician and Study chair, in accord with the Cancer Center Statistics (CCS) Standard Operating procedures, availability of data for secondary endpoints, and the level of data maturity. It is anticipated that the earliest date in which the results will be made available via a manuscript, abstract, or presentation format is when 45 patients have either had confirmed-progression or been followed for at least 6 months. Subgroup analysis will be included for this primary endpoint to assess known prognostic factors such as performance status at baseline and age. Additionally, while no expected difference is anticipated, subset analysis will also be conducted for the primary endpoint to assess if there was any difference in patients treated via photons vs. protons.

16.31 Primary Endpoint:

16.311 Definition: The primary endpoint of this trial is the proportion of Grade-IV MGMT un-methylated patients that experience confirmed-progression-free survival at 6 months from the time of craniotomy. All Grade IV MGMT un-methylated patients meeting eligibility criteria who have signed a consent form and who have begun RT treatment will be evaluable for the endpoint. All eligible patients will be followed until death or a maximum of 5 years. Time to confirmed-progression is defined as the time from initial surgery to the earliest date documenting confirmed-progression. If a patient dies without documentation of disease progression, the patient will be considered to have had tumor

progression at the time of death. If a patient is declared to be a major treatment violation, the patient will be censored on the date the treatment violation was declared to have occurred. In the case of a patient starting treatment and then never returning for any evaluation, the patient will be censored for progression on the last day of therapy.

- 16.312 Estimation: The proportion of CPFS6 successes and associated 95% confidence intervals will be estimated using Kaplan-Meier analysis methods.
- 16.313 Over Accrual: If more than the target number of patients are accrued, the additional patients will not be used to evaluate the stopping rule or used in any decision making processes; however, they will be included in final point estimates and confidence limits.

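### Section 16.311 censors treatment violators and never-returners for an endpoint decided by a count; this discards failures the trial can observe and lets the Kaplan-Meier figure disagree with the decision

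*Combined protocol and SAP*

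**What the plan says.** - **Who is in the set.** Section 16.11 says that eligible, consented un-methylated patients who have begun "PET image-guided dose escalation RT will be evaluable for the endpoint". Section 16.311 repeats this for patients "who have begun RT treatment will be evaluable for the endpoint" and has all eligible patients followed until death or 5 years. Section 16.21 defines endpoint-evaluable by receipt of the study RT. None of these removes a later violator or a lost patient.
- **Censoring.** Section 16.311 adds: "If a patient is declared to be a major treatment violation, the patient will be censored on the date the treatment violation was declared". A patient who starts treatment and is never seen again is censored at the last day of therapy: "never returning for any evaluation, the patient will be censored for progression on the last day of therapy". Death without documented progression counts as progression.
- **Decision.** Stage 1 needs 16 successes in the first 25 "evaluable patients that have been followed for at least 6 months". Stage 2 applies after 45 are "accrued to this study and followed for at least 6 months, if 30 or more successes are observed in the first 45 evaluable patients". Section 16.24 treats the number of successes as binomial.
- **Estimate.** Section 16.312: "The proportion of CPFS6 successes and associated 95% confidence intervals will be estimated using Kaplan-Meier analysis methods".
- **Timing of results.** Section 16.3 gives the earliest release as "when 45 patients have either had confirmed-progression or been followed for at least 6 months".
- **Extra accrual.** Section 16.22 plans 5 more un-methylated patients and names major treatment violation among the reasons. No passage defines that term.

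**The concern.** A count needs each of the 25 or 45 patients to be a success or not. Censoring is a third state, and the plan does not say how it maps to the count. The more serious part concerns violators. They remain evaluable and in follow-up, so the trial will usually know whether they progressed or died by 6 months. Censoring them at the violation date discards that information from the estimate of the primary proportion, and from the decision as well if the sentence is applied there. For never-returners the 6-month status may really be unknown, and the count has no explicit rule for that.

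Two things are at stake. The reported CPFS6 can fall on the other side of 30/45 = 66.7% from the decision. And because this is a single-arm trial in which outcomes are visible, an unstated scoring rule could be settled after the results are known.

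**Working it through.** **1. The plan's own figures.** Inputs from 16.21: continue if X25 ≥ 16, declare success if X45 ≥ 30, null rate 0.60, alternative 0.725. Let D(p) be the chance of declaring success:

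D(p) = Σ (x = 16 to 25) P[Bin(25, p) = x] × P[Bin(20, p) ≥ 30 − x].

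D(0.60) = 0.195 and D(0.725) = 0.804. The other four columns of the 16.24 table also reproduce. The design figures are correct, provided that all 45 patients are classified.

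**2. Estimate against decision.** Take 29 successes, 14 failures and 2 patients censored before 6 months (illustrative).
- Count: 29/45 = 64.4%. The rule is not met.
- Kaplan-Meier, both censored before the first event: 43 at risk, 14 events, (42/43)(41/42)…(29/30) = 29/43 = 67.4%.
- Kaplan-Meier, both censored after the last event: 31/45 = 68.9%.
- Other censoring dates before 6 months lie between these values.

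Every version is above 66.7%, although the count fails. If the two were violators who later progressed or died before 6 months, they are known failures, and 64.4% is the observed proportion.

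**3. One patient is enough.** With 29 successes, 15 failures and 1 unresolved patient, the count is 29/45 (fails) or, if that patient is scored a success, 30/45 (passes). At stage 1, 15 successes, 9 failures and 1 unresolved give 15/25 (stop) or 16/25 (continue).

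**4. False-positive rate if such patients were dropped and replaced.** The documents give neither a loss rate nor a prognosis, so both are assumed: k per 45, q = k/45, success rate s in this group. Holding the overall rate at the null 0.60, the patients who are counted have p = (0.60 − q·s)/(1 − q). For k = 1 and s = 0.30: (0.60 − 0.0067)/0.9778 = 0.607. D(p) is then:

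| s | k = 1 | k = 2 | k = 3 | k = 5 |
|---|---|---|---|---|
| 0.60 (average) | 0.195 | 0.195 | 0.195 | 0.195 |
| 0.50 | 0.204 | 0.213 | 0.222 | 0.244 |
| 0.30 | 0.221 | 0.250 | 0.283 | 0.360 |

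The value k = 5 is illustrative. The 5 extra patients in 16.22 are a projection for several reasons together and do not bound the losses.

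**5. Price of scoring unknown status as non-success.** If the stated rate applies only to patients whose status is known, p becomes 0.725(1 − q) or 0.60(1 − q).

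| | k = 1 | k = 2 | k = 3 | k = 5 |
|---|---|---|---|---|
| Power | 0.735 | 0.656 | 0.570 | 0.396 |
| False-positive rate | 0.150 | 0.113 | 0.083 | 0.041 |

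**6. The benchmark.** Section 16.21 gives a combined control rate of 59.3% for 81 plus 14 patients. With 81 + 14 = 95 as denominator, no simple count yields it (56/95 = 58.9%, 57/95 = 60.0%), while 48/81 = 59.3%. A Kaplan-Meier estimate is also possible. The documents do not say how the controls were counted.

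**The case against.** The strongest reply is that the count already has a workable reading. Evaluability rests on having begun study RT, the denominators are fixed, and the rule counts observed successes, so a patient of unknown status is not a success. The six-month follow-up wording in 16.211 and 16.212 can only be a timing condition: taken literally, it would also exclude a patient who dies at month 3. The sentence in 16.3 concerns release of results, not membership of the 45. The censoring sentences follow the definition of time to confirmed progression and recur in 16.322, so they naturally serve the time-to-event estimate. Section 16.313 separates decision from estimate on purpose. Section 11.414 lists failure to return because of death or deterioration as progression. And losses should be few: deaths are events, Event Monitoring continues, and imaging is obtained from local physicians (13.5, 18.13).

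Most of this stands. A reader might infer that the plan drops or replaces these patients. The text does not support that. Section 16.22 is an accrual projection that never mentions replacement, and it can be read as covering violators who never receive study RT and so are not endpoint-evaluable (13.3, 16.21).

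Two things survive. The censoring sentences sit in the definition of the primary endpoint and are not limited to the estimate. Even if they were, the estimate of the primary proportion would still discard a violator's observed progression or death. Nor does 11.414 settle the scoring: confirmed progression also needs more than 3 months since RT, radiologic progression on central review and clinical progression, which cannot be documented in a living patient who never returns.

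**Conclusion.** The point holds at moderate severity and with moderate confidence. What is firm is that 16.311 keeps violators evaluable and in follow-up yet censors them, that the decision rule has no censored state, and that the 16.312 estimate can therefore contradict the decision.

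A reader might go further and infer that the true false-positive rate exceeds 0.20. The documents do not support that. It would need such patients to be dropped or replaced, which no passage states, and to do worse than average, for which no figure is given. The 30% scenario has no source; at 50% the inflation is modest, and at average prognosis it is nil. The 16.24 table is not in error. The likely effect is small, but the decision margin is a single patient and the rule can be stated now at little cost.

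**What to change.** 1. **16.311:** do not censor major treatment violators for the primary endpoint. Use their observed 6-month status, and define the term.
2. **16.21:** state that the first 25 and 45 are all eligible un-methylated patients who begin study RT, with no replacement after RT starts; that the six-month follow-up wording is a timing condition; and that a patient not documented alive and free of confirmed progression at 6 months is not a success. Reconcile this with 11.414, and with 16.22, where the extra 5 would cover patients who are ineligible or never start study RT.
3. **16.312:** report x/45 beside the decision, with an exact interval that allows for the two stages (for 30/45, ordering stage-1 stops below all stage-2 outcomes: 51.6% to 80.8%). Keep the censored Kaplan-Meier estimate, including over-accrued patients under 16.313, as a sensitivity analysis.
4. **Benchmark:** state how the 59.3% was counted and recount the controls under the same rule.

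The cost is wording plus a recount of existing control data, with no added patients or visits. The reported estimate becomes less favourable. If 72.5% was meant for returning patients only, power falls as in step 5 of the working, and substantially so with several unresolved patients. Without a matched benchmark the rule is conservative. Using violators' observed status limits this loss to patients whose status is truly unknown.

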16.32 Definitions and Analyses of Secondary Endpoints

Subgroup analysis will be included as appropriate for these secondary endpoints to assess known prognostic factors such as performance status and age at baseline. Additionally, subset analysis will also be conducted for the primary endpoint to assess whether there was any difference in patients treated via photons vs. protons. To control for multiple testing the false discovery rate (FDR) [75], which is the expected proportion of false discoveries amongst the rejected hypotheses, will be used at a 0.05 level.

- 16.321 Compare progression free survival at 12 months for Grade III patients after radiation therapy targeting volumes designed with both ¹⁸F-DOPA PET and conventional MR image information with historical controls from Mayo Clinic Rochester patients, including those on clinical trials.

While both Grade III and IV glioma patients will be enrolled on this clinical trial, Grade III astrocytomas are relatively rare and not commonly studied in NCCTG or Mayo Clinic trials. Grade III patients are included in our prospective dose-escalation trial given their overall poor prognosis and the often limited contrast enhancement observed in these tumors. The target definitions will be similar to those described in section 7.0, Table 1. The progression-free survival at 12 months will be compared to historical controls treated at Mayo Clinic. Given the small numbers of patients with Grade III glioma anticipated (4 endpoint-evaluable patients as of 2/16/2017) on this prospective trial; this analysis will be hypothesis generating. The proportion of successes will be estimated by the number of successes divided by the total number of Grade-III evaluable patients. Confidence intervals for the true success proportion will be calculated according to the approach of Duffy and Santner (1987).

16.322 Confirmed-Progression Free Survival

We will analyze the confirmed-progression free survival time to event data combined with the confirmed-progression free survival data from the Mayo Clinic patients treated either with standard of care RT+TMZ then TMZ-alone or on studies N057K or N0874. These Mayo Clinic patients will be considered to be a control group. The distributions of confirmed-progression free survival times and comparisons between these two groups will be estimated using the method of Kaplan-Meier

[76]. Time to disease progression is defined as the time from initial surgery to the earliest date documenting confirmed-progression. If a patient dies without documentation of disease progression, the patient will be considered to have had tumor progression at the time of death. If a patient is declared to be a major treatment violation, the patient will be censored on the date the treatment violation was declared to have occurred. In the case of a patient starting treatment and then never returning for any evaluation, the patient will be censored for progression on the last day of therapy. This analysis will be conducted split by MGMT-methylation status of the patients and historical control.

16.323 Overall Survival

Compare patient outcomes including overall survival after radiation therapy targeting volumes designed with both ^{18}F -DOPA PET and conventional MR image information with historical controls from Mayo Clinic Rochester patients. As described above for confirmed-progression free survival, we will analyze both historical control patients and our prospective dose escalation patients for overall survival. Survival time is defined as the time from initial surgery to death due to any cause. The distributions of survival times and comparisons between these two groups will be estimated using the method of Kaplan-Meier [76].

16.324 Quality of Life

Evaluate quality of life after radiotherapy treatment targeting dose escalated volumes defined to include high ^{18}F -DOPA PET uptake. Quality of life (QOL) will be compared to high-grade glioma patients treated on previous North Central Cancer Treatment Group protocols. QOL and cognitive function will be evaluated with the MD Anderson Symptom Inventory Brain Tumor Module (MDASI-BT) and Mini-Mental Status Exam (MMSE) questionnaires at baseline and at each MRI evaluation up to 6 evaluations to capture the quality of life profile and correlate findings with radiologic and clinical progression as well as time points used on prior studies to allow historical comparisons. The main QOL analysis will be the change from baseline to first subsequent MRI timepoint in the overall score from the MDASI-BT. All other QOL analysis will be exploratory and may include change percent from baseline to all timepoints using t-tests and generalized linear models to test for changes at each time point and non-zero slope respectfully.

16.325 Adverse Events

Determine acute and late effect toxicity after radiotherapy treatment targeting dose escalated volumes defined to include high ^{18}F -DOPA PET uptake. The rate of acute and late treatment-related toxicities for newly diagnosed high-grade glioma patients treated with ^{18}F -DOPA PET image-guided dose escalation will be determined, with acute RT toxicities graded using Common Terminology Criteria for Adverse Events (CTCAE) v4.0 (available at <http://ctep.cancer.gov>), and late toxicities reported using the RTOG/EORTC late toxicity criteria [71]. Patients will be considered evaluable for adverse events if they receive ^{18}F -DOPA PET or ^{18}F -DOPA PET image-guided dose escalation RT.

16.326 Compare confirmed-progression free survival at 12 months for Grade IV MGMT-methylated patients after radiation therapy targeting volumes designed with both ^{18}F -DOPA PET and conventional MR image information with historical controls from Mayo Clinic Rochester patients, including those on clinical trials.

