3.0 Patient Eligibility

3.1 Inclusion Criteria

- 3.11 Age ≥ 18 years.
- 3.12 Histologically confirmed newly diagnosed grade IV malignant glioma.
Note: as of addendum 8, Grade III patients are no longer being enrolled.
- 3.13 CT simulation, immobilization, MRI and PET imaging, treatment planning, and all follow-up MRI and PET scans to be performed at Mayo Clinic Rochester.
Note: The actual radiation therapy treatments and follow-up other than imaging can be performed at Mayo Clinic Rochester, Northfield, LaCrosse, Mankato, Eau Claire, or Albert Lea.
- 3.14 Provide written informed consent.
- 3.15 Ability to complete questionnaire(s) by themselves or with assistance.

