12.0 Descriptive Factors

- 12.1 Corticosteroid therapy at study entry: Yes (specify dose) vs. no
- 12.2 Histologic type of primary tumor: Oligodendroglioma vs. oligoastrocytoma vs astrocytoma vs other, specify
- 12.3 Histologic grade of primary tumor: 3 vs. 4
- 12.4 ECOG PS (see Appendix I): 0 vs. 1 vs. 2 vs. 3
- 12.5 Neurologic deficit: Yes vs. no
- 12.6 History of seizures: Yes vs. no
- 12.7 Prior surgical resection or biopsy: Yes vs. no
- 12.8 Age ≤ 70 vs. > 70
- 12.9a MGMT: Methylated vs. Unmethylated vs. Not available
- 12.9b Family history of brain tumor: Yes vs. no
If yes, check all that apply:
 Father/Mother
 Brother/Sister
 Child
 Other (list: _____)

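### CPFS and OS are compared with non-randomised historical controls by Kaplan-Meier only, with no adjusted estimate, and the OS population is left unresolved

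*Combined protocol and SAP*

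**What the plan says.** Section 16.322 treats Mayo Clinic patients given standard chemoradiation, in routine care or on N057K or N0874, as a control group. It states: "The distributions of confirmed-progression free survival times and comparisons between these two groups will be estimated using the method of Kaplan-Meier". Section 16.323 repeats this for OS: "The distributions of survival times and comparisons between these two groups will be estimated using the method of Kaplan-Meier". Neither section names a test, an effect measure, a regression model, matching or weighting. Section 16.32 nevertheless applies a false discovery rate of 0.05, so p-values are intended.

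Two provisions bear on case mix. Section 16.32 says: "Subgroup analysis will be included as appropriate for these secondary endpoints to assess known prognostic factors such as performance status and age at baseline". Section 16.322 ends: "This analysis will be conducted split by MGMT-methylation status of the patients and historical control". Section 16.323 does not repeat that sentence.

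The descriptive factors in section 12.0 include age (cut at 70), performance status ("ECOG PS (see Appendix I): 0 vs. 1 vs. 2 vs. 3"), MGMT ("MGMT: Methylated vs. Unmethylated vs. Not available") and surgery ("Prior surgical resection or biopsy: Yes vs. no"). Criterion 3.12 requires "Histologically confirmed newly diagnosed grade IV malignant glioma".

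**The concern.** These are the plan's time-to-event comparisons with controls (goals 2.22, 2.26 and 2.27). Without randomisation, case mix is the main rival explanation for any difference. Two Kaplan-Meier curves, or a log-rank test added to them, cannot separate case mix from a treatment effect. The plan itself calls age and performance status prognostic and lists both, but does not use them in the main contrast.

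Two further points make this harder to resolve later. Section 1.8 says that PFS differs strongly by MGMT status and that the trial's MGMT mix shifted, yet which patients enter the OS comparison is not settled. And item 12.7, as worded, should be answered yes for essentially every eligible patient, because histology requires tissue. It therefore cannot separate biopsy-only from resected patients, a distinction that section 7.41 does draw.

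**Working it through.** **The plan's own figures.** No sample size, event count or power is stated for the CPFS or OS comparison, so there is nothing to reproduce there. The primary design does reproduce. An exact two-stage binomial calculation (stop at 15 or fewer of 25; success at 30 or more of 45) gives 0.195 at a true rate of 60% and 0.804 at 72.5%, as in section 16.24. That rule tests a fixed 60% and uses none of the comparisons discussed here.

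**OS population, passages side by side.**
- Goal 2.22: OS, with no MGMT or grade limit. Goals 2.25 to 2.27 are MGMT-specific.
- Section 16.11: from Addendum 8, only un-methylated Grade IV patients enter the analysis that follows.
- Section 16.322: CPFS is split by MGMT status. Section 16.326: a comparison for methylated patients. Both conflict with 16.11.
- Section 16.323: refers back to CPFS for the two cohorts and is silent on MGMT.

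OS could therefore be un-methylated only, split by MGMT, or pooled; the text does not decide. Nor does it say whether the few Grade III patients (4 evaluable in 16.321) are included.

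**Precision, un-methylated comparison.** Inputs: 45 trial patients and 81 + 14 = 95 controls (16.21), with 80% having events (assumed). Events: 0.8 × 45 = 36 and 0.8 × 95 = 76. SE(log HR) = √(1/36 + 1/76) = 0.202. The 95% CI is the HR multiplied or divided by exp(1.96 × 0.202) = 1.49.

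**Case mix within un-methylated patients.** Simulated Cox analyses, 45 versus 95, latest 20% of times censored, one unfavourable binary factor. Shares and prognostic HRs are assumed. The probability is that of a nominally significant benefit (z < −1.96), before any FDR correction.

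| Factor, trial vs control | Prognostic HR | True HR | Unadjusted HR (prob.) | Adjusted HR (prob.) | SE, unadjusted / adjusted |
|---|---|---|---|---|---|
| 10% vs 20% | 1.5 | 1.00 | 0.96 (4%) | 1.00 (2%) | 0.204 / 0.206 |
| 10% vs 30% | 2 | 1.00 | 0.88 (8%) | 1.00 (2%) | 0.205 / 0.212 |
| 20% vs 40% | 2 | 1.00 | 0.88 (8%) | 1.01 (2%) | 0.205 / 0.211 |
| 40% vs 20% | 2 | 0.63 | 0.74 (30%) | 0.63 (57%) | – |

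The nominal false-benefit rate is 2.5%. The true HR of 0.63 is ln(0.725)/ln(0.60), the design's two rates under proportional hazards. In the last row the imbalance runs against the trial and hides part of a real effect.

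**MGMT, if OS is pooled.** Un-methylated share among trial patients of known status: 45/(45 + 22) = 67% (16.33). The control mix is not stated; the institution's is about 60% (16.23). With no treatment effect and an assumed MGMT HR of 1.5 to 2.5, the large-sample pooled HR is:

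| Controls un-methylated | Pooled HR |
|---|---|
| 55% | 1.05 to 1.11 |
| 60% | 1.03 to 1.06 |
| 65% | 1.01 to 1.02 |
| 70% | 0.99 to 0.98 |
| 80% | 0.95 to 0.89 |

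**Model support.** Un-methylated: 0.8 × 140 = 112 events; with 4 parameters, 112/4 = 28 each. Methylated: 25 planned trial patients (16.22), control count not given. Assuming 40 to 63 controls (63 = 95/0.6 × 0.4) and 60% to 80% with events gives 0.6 × 65 = 39 to 0.8 × 88 = 70 events, or about 10 to 18 per parameter.

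**The case against.** The controls are closer than most historical series. They share the institution, MR target definitions, imaging schedule and radiology review, and 81 of the 95 un-methylated controls were themselves trial participants. That stands, but shared methods do not balance age, performance status or resection.

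The planned subgroups could compare trial and control patients within levels of age and performance status, which would condition on those factors. This is partial mitigation. It is to be done only where judged appropriate, no method is given, extent of resection is not named, and no single adjusted estimate results.

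The illustrated bias is small beside a CI factor of 1.49, and the largest effects need a 20-point imbalance in a factor with HR 2. That is fair. It keeps this a cheap improvement to secondary analyses.

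A reader might infer that OS is certainly pooled over MGMT status. The documents do not support that: the back-reference in 16.323 may carry the split over, and 16.11 may exclude methylated patients altogether. A reader might also infer that surgical extent is not recorded. Only the wording of 12.7 is known; the On-Study form is not in the documents, and section 7.41 suggests that the information exists.

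**Conclusion.** The concern holds for the secondary comparisons. The plan offers no adjusted trial-versus-control estimate for CPFS or OS, and its passages on the OS population conflict. The change should be made, but it is not critical: the 30-of-45 rule is untouched, and the MGMT split already protects CPFS on that factor.

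The sizes rest on assumed shares, prognostic HRs and event fractions. Within un-methylated patients, case mix moves a null HR to 0.96 to 0.88, or a true 0.63 to 0.74. It would be tempting to conclude that the comparison favours the regimen, or that pooling OS over MGMT works against it. Neither follows. The documents give no age, performance-status or resection mix for either cohort and no MGMT mix for the controls, and the pooled HR falls on either side of 1 over plausible control mixes.

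**What to change.** 1. Reconcile 16.11 with 16.322, 16.323 and 16.326. State that OS is for Grade IV patients and is analysed within, or stratified by, MGMT status. Describe patients of unknown status separately unless controls of unknown status exist.

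2. In 16.322 and 16.323 keep the Kaplan-Meier curves and pre-specify a Cox model that gives the trial-versus-control hazard ratio with its 95% CI and a check of proportional hazards. For un-methylated patients use four parameters: group, age (continuous), ECOG PS as one term, and biopsy only versus resected. Use the p-value from this model in the FDR procedure. For methylated patients label the adjusted model exploratory.

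3. Obtain biopsy-only versus resected status from existing records in both cohorts, and word 12.7 that way. If it cannot be obtained for controls, adjust for age and ECOG PS and say so.

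Cost: SAP wording and some chart abstraction, probably modest, although the documents do not confirm that ECOG PS or surgical extent is on file for all controls. The SE rises slightly (1% to 3% in the no-effect settings above). The model brings its own assumptions, and unmeasured confounding remains.
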